9.5.6.2. Eastern Cooperative Oncology Group Performance Status

Descriptive statistics will be provideded and baseline value, value after baseline and changes in value from baseline will be summarized by time points. Formal hypothesis test will not be performed.

9.5.6.3. Vital signs

Continuous descriptive statistics will be provided and assessment results will be summarized overall by time points. In addition, changes in continuous parameters from baseline will be summarized. For categorical parameters, n and proportion will be presented. Formal hypothesis test will not be performed.

9.5.6.4. Echocardiogram

Continuous descriptive statistics will be provided and assessment results will be summarized overall by time points. In addition, changes in continuous parameters from baseline will be summarized. For categorical parameters, n and proportion will be presented. Formal hypothesis test will not be performed.

9.5.6.5. Dermatologic examination evaluation results

Descriptive statistics will be provided for summary of evaluation results of dermatologic examination. Formal hypothesis test will not be performed.

9.5.6.6. Clinical laboratory parameters

Continuous descriptive statistics will be provided and assessment results will be summarized overall by time points. In addition, changes in continuous parameters from baseline will be summarized. For categorical parameters, n and proportion will be presented. Formal hypothesis test will not be performed.

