2.2. Secondary objective

- To assess objective response rate (ORR) by independent radiologic review using RECIST v1.1-GIST-specific criteria
- To assess disease control rate (DCR) by independent radiologic review
- To assess PFS based on Investigator assessment
- To assess overall survival (OS)
- To compare the safety profile of DCC-2618 (ripretinib, ZL-2307) to the safety profile of sunitinib
- To assess pharmacokinetic characteristics of DCC-2618 (ripretinib, ZL-2307)

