6.11.8. Clinical laboratory tests

Blood and urine samples will be collected and analyzed according to Table 1 (Schedule of Assessments). All blood samples must be collected when the patient is in a sitting or supine position. If laboratory test abnormality is clinically significant, it should be reported as AE (Section 7.7.1). All laboratory test results must be graded according to toxicity definition in Common Terminology for Adverse Events of National Cancer Institute (NCI CTCAE), v5.0.

Items of safety laboratory tests refer to Table 1111.

Table 11: Safety laboratory tests

Blood biochemistry	Blood routine	Routine urine test	
Blood glucose	Haemoglobin	Protein urine	
Blood urea nitrogen/urea	Platelet	Urine occult blood	
Creatinine	White blood cells	Specific gravity	
Sodium	Reticulocyte	Urine ketone body	
Potassium	Classification (absolute count):	Urine Glucose	
Calcium	Neutrophil		
Magnesium	Lymphocyte		
Phosphonium	Monocyte		
Bilirubin total and Bilirubin direct	Coagulation tests ¹		
Alkaline phosphatase	Activated partial thromboplastin time		
Glutamic-oxaloacetic transferase	Pro-thrombin Time		
Alanine transaminase	International Normalized Ratio		
Lactate dehydrogenase			
Total protein			
Albumin			
Creatine phosphokinase			
Globulin			
Triglyceride			
Lipase			
Thyroid test			
Thyroid stimulating hormone (TSH)			
Free triiodothyronine (FT3)			

Blood biochemistry	Blood routine	Routine urine test
Free thyroxine (FT4)		

1. For patients who take anticoagulant, test will be carried out according to Table 1 (Schedule of Assessments). If the dose of anticoagulant changes during the study, monitoring of coagulation function should be increased if clinically suitable.

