7.7. Additional Considerations on Adverse Events

7.7.1. Clinical Significance

Laboratory test, ECG, physical examination and vital signs will be evaluated during the study and clinically significant abnormalities should be recorded as AEs. If possible, disease diagnosis should be first used as the name of adverse events (e.g., urinary tract infection and anemia). If the diagnosis is unable to be confirmed, abnormal test findings will be reported as AE (e.g., bacterial in urine or haemoglobin decreased). Once the diagnosis is confirmed with the follow up information, the symptoms and sign should be replaced with diagnosis accordingly. If subjects meet one or several of the following conditions, abnormal study assessment will be regarded as clinically significant:

- Persistent deterioration from baseline, accompanied with corresponding symptoms or signs.
- Further diagnostic tests or drug/surgical therapies required.
- Leading to change in dose of the study drug, such as drug discontinuation or treatment termination.

Repeat testing to determine whether the result is abnormal, in the absence of any of the above criteria, does not necessarily meet clinically significant criteria. The determination of whether the study assessment results are clinically significant must be made by the Investigator.

A laboratory abnormality judged to be Grade 4, in itself, may not constitute an SAE unless the clinical status of the patient indicates a life-threatening AE.

Symptoms of the disease under study must not be recorded as AEs as long as they are within the normal day-to-day fluctuation or expected progression of the disease, including significant worsening unless the deterioration was unexpected, and are part of the efficacy data to be collected in the study.

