7.8. Definition of Serious Adverse Event(SAE)

An AE is considered serious if it meets any of the following:

- Results in death (regardless of cause, that occurs during participation in the study or occurs after participation in the study and is suspected of being a delayed toxicity due to administration of the study drug)
- Is life threatening (an event/reaction in which the patient was at risk of death at the time of the event/reaction; it does not refer to an event/reaction which hypothetically might have caused death if it were more severe)

• Requires inpatient hospitalization or prolongation of existing hospitalization

Zai Lab

- Results in persistent or significant disability/incapacity
- Results in congenital anomaly/birth defect
- Important medical events that may not result in death, are life-threatening, or require hospitalization may be considered serious when, based upon appropriate medical judgment, they may jeopardize the patient and may require medical or surgical intervention to prevent one of the outcomes (i.e. allergic bronchospasm requiring intensive treatment in an emergency room or at home, blood dyscrasias or convulsions that do not result in inpatient hospitalization, or the development of drug dependency or drug abuse).

The following were not to be reported as SAEs:

- Any outcome, including death, due to progression of the patient's primary tumor disease as assessed by the investigator.
- Hospitalization or prolonged hospitalization due to economic issue or for purpose of reimbursement only.
- Elective surgery scheduled prior to the start of study treatment.
- Prescription or study-related examinations can be carried out only during hospitalization for hospital management reasons

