7.9. Adverse Events of Special Interest (AESIs)

An AESI is an AE (serious or nonserious) of scientific and medical concern specific to study drug, for which ongoing monitoring and immediate notification by the Investigator to the Sponsor is required. Such AEs may require further investigation to characterize and understand them. AESIs may be added or removed during a study by a protocol amendment.

The following AEs are considered AESIs:

- Squamous cell carcinoma of skin
- Actinic keratosis
- Keratoacanthoma

7.10. **Adverse Events Reporting Period**

The AE (including SAEs and AESIs) reporting period begins from the time that the patient provides informed consent through and including 30 days after the last dose of the study drug, or until a new anti-tumor therapy is initated, which occurs first. For any SAEs or AESIs occurring after this reporting period, it will be reported only when a causal relationship between the SAEs or AESIs and study product is suspected by the study drug.

7.11. Adverse Event, Serious Adverse Event, and Adverse Event of Special Interest Reporting Requirements

Each patient must be carefully monitored for the development of any AEs. This information must be obtained in the form of non-leading questions (e.g. "How are you feeling?") and from signs and symptoms detected during each examination, observations of study personnel, and spontaneous reports from patients. All AEs (serious and non-serious) spontaneously reported by the patient and/or in response to an open question from study personnel or revealed by observation, physical examination or other diagnostic procedures must be recorded.

When possible, signs and symptoms indicating a common underlying pathology must be noted as 1 comprehensive event. Accompanying signs or symptoms (e.g. abnormal laboratory values) must not be reported as additional AEs. If a diagnosis is unknown, one or more symptoms may be reported as separate AEs. If an underlying diagnosis is subsequently determined for the reported symptom(s), then the reported symptom(s) term(s) must be revised to be "attributed" or "due" to the diagnosis.

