9.3. Analysis Population

The following populations will be used for analysis: all patients intent-to-treat (ITT) population, KIT exon 11 mutation intent-to-treat (Ex11 ITT) population, safety population, PK population, all patients per-protocol (PP) population and KIT exon 11 mutation per-protocol (Ex11 PP) population.

ITT population is defined as all randomized patients. Patients in the population will be analyzed according to treatment they will receive.

KIT exon 11 mutation intent-to-treat (Ex11 ITT) population is defined as all patients with KIT exon 11 mutation at randomization. Patients in the population will be analyzed according to

treatment they will receive.

Safety analysis population is defined as all subjects who were randomly assigned and received at least one dose of study drug. Safety population will be used for all safety analyses and treatment assignment will be based on the actually received initial study treatment.

PK population will include all randomized subjects who have received at least one dose of DCC-2618 (ripretinib, ZL-2307) and have at least a non-missing plasma PK concentration report of DCC-2618 (ripretinib, ZL-2307) and DP-5439.

PP population is defined as all patients in ITT population who have at least one tumor assessment after baseline, meet all inclusion criteria, don't violate any exclusion criteria and don't have any significant study protocol violation/deviation that are considered to influence the integrity of the study. Efficacy analysis in the PP population is supportive and the analysis in treatment groups will be based on the actually received treatment. Patients who violate the study protocol and excluded from the PP population will be identified and recorded before locking the database.

KIT exon 11 mutation per-protocol (Ex11 PP) population is defined as all patients in Ex11 ITT population who have at least one tumor assessment after baseline, meet all inclusion criteria, don't violate any exclusion criteria and don't have any significant study protocol violation/deviation that are considered to influence the integrity of the study. Efficacy analysis in the Ex11 PP population is supportive and the analysis in treatment groups will be based on the actually received treatment. Patients who violate the study protocol and excluded from the Ex11 PP population will be identified and recorded before locking the database.

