9.5.6.1. AEs

AEs in the safety population will be summarized with the number of events and proportion of patients according to system organ class (SOC) and preferred term. All tables will only include TEAE. "Treatment emergent" is defined as any AEs occurring during the first dose of the investigational drug and up to 30 days after the last dose of the investigational drug. However, the listing will include all AEs collected.

Toxicity grade of AE will be classified with NCI-CTCAE V5.0 (See Table 12). If a patient has the same SOC or preferred term evet for several times, only the most severe event will be summarized in the tables for that SOC and preferred term. AEs grade ≥ 3 will be summarized. Missing toxicity grade will not be imputed.

SAEs, AEs and AESIs that lead to dose reduction or discontinuation and AEs will be also analyzed.

Formal hypothesis test of incidence of AE will not be performed.

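### Drug-related SAEs and skin AESIs arising more than 30 days after the last dose would reach only a listing, not the by-arm safety tables

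*Combined protocol and SAP*

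**What the plan says.** **Purpose and population.** A secondary objective (section 2.2) is: "To compare the safety profile of DCC-2618 (ripretinib, ZL-2307) to the safety profile of sunitinib". Section 9.2.2.2 lists the incidence of TEAEs, of AESIs and of SAEs among the safety endpoints. In the safety population (section 9.3), "treatment assignment will be based on the actually received initial study treatment". Section 5.11 confirms that the trial is open-label.

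**Late events.** Section 7.9 names three AESIs, all skin lesions: squamous cell carcinoma, actinic keratosis and keratoacanthoma. Under section 7.10, routine AE reporting stops 30 days after the last dose, or earlier if a new anti-tumour therapy starts. Beyond that: "For any SAEs or AESIs occurring after this reporting period, it will be reported only when a causal relationship" to study product is suspected. Section 9.5.6.1 then says "All tables will only include TEAE", ends the treatment-emergent window 30 days after the last dose, and sends all other collected events to the listing.

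**Laboratory data.** Section 6.11.8: "All laboratory test results must be graded according to toxicity definition in Common Terminology for Adverse Events". Section 9.5.6.6: "Continuous descriptive statistics will be provided and assessment results will be summarized overall by time points". It adds changes from baseline and, for categorical parameters, counts and proportions. An abnormal result becomes an AE if clinically significant, and under section 7.7.1 "The determination of whether the study assessment results are clinically significant must be made by the Investigator".

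**Deaths.** Among the items that section 7.8 excludes from SAE reporting is: "Any outcome, including death, due to progression", on the investigator's assessment. Section 7.11 has such deaths recorded in the eCRF. Section 9.5.6 names no table of deaths.

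**The concern.** The protocol makes an explicit exception so that suspected late toxicity is still captured, and then applies a table rule that removes it from the comparison. The SAE definition in section 7.8 itself allows for delayed toxicity: a death after participation counts if it is suspected to be a delayed effect of study drug.

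The AESIs are the events that section 1.3.2.1.3 singles out because their relation to the drug is unknown. If some are diagnosed after the 30-day window, the by-arm incidence of SAEs and AESIs will be too low by exactly those cases. A reader would have to rebuild the count from a listing, without denominators and without a comparison fixed in advance. In an open-label trial it is better to fix that comparison before the data are seen.

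**Working it through.** The plan gives no figure for this point, so the main check sets the sections side by side.

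**1. What is collected late.** Section 7.10: SAEs and AESIs with suspected causality, after the reporting period.

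**2. What is tabulated.** Section 9.5.6.1: only events up to 30 days after the last dose.

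**3. Where the gap lies.** The two windows are not identical. If a patient starts a new therapy on day 15, the reporting period ends then, but a related SAE on day 20 is still within the treatment-emergent window and is tabulated. The gap is therefore suspected-related SAEs and AESIs after day 30. They are collected, they belong to an endpoint in section 9.2.2.2, and they are tabulated nowhere.

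**4. Size.** The number of late events is not given and cannot be derived. Two pieces of arithmetic show the scale.

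- Phase 1 AESI counts (section 1.3.2.1.3), with the 256 enrolled patients of section 1.3.2.1.2 as denominator: 15/256 = 5.9%, 32/256 = 12.5%, 7/256 = 2.7%. These reproduce the stated percentages. Timing relative to the last dose is not reported, so they say nothing about how many were late.
- Assume all 49 patients per arm (section 9.1) are dosed. One patient whose first event of a type is late changes that arm's incidence by 1/49 = 2.0 percentage points. If the phase 1 rate of squamous cell carcinoma applied to the ripretinib arm, 49 × 15/256 = 2.9 patients would be expected. One late case on top of 3 changes 3/49 = 6.1% to 4/49 = 8.2%. This is an illustration, not a forecast.

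**5. How well late events can be found.** In Table 1 the last scheduled dermatologic examination is at the EOT visit, within 7 days of the last dose. A safety telephone call follows at 30 ± 5 days. The later calls, every two months, are for new anti-tumour therapy and survival data (section 6.4). Late AESIs would therefore come from unscheduled or spontaneous reports.

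**6. Laboratory grades.** Grade is assigned to every result (6.11.8), but 9.5.6.6 names no worst-grade, grade 3–4 or shift table. Its provision for categorical parameters could carry grades. Table 10 in section 5.4.2 recognises grade 3–4 values that are not clinically significant; these need not become AEs, so no named table is certain to show them.

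**7. Deaths.** All-cause death is the OS event (9.5.5.2.2) and a PFS event (9.5.5.1). Deaths of unknown cause, or whose link to progression cannot be determined, are SAEs (7.11). What is not named is a summary of deaths during and shortly after treatment, by cause.

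**The case against.** **No data are lost, and a 30-day cut-off has a purpose.** Every collected event is listed, and later events are increasingly mixed with the effects of the next therapy. Both points stand. They argue for keeping the TEAE tables and showing late events separately, not for leaving them untabulated.

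**Section 9.2.2.2 names SAEs and AESIs separately from TEAEs, so their incidence may not be meant to stop at day 30.** That is a possible reading, but it conflicts with the all-tables rule in 9.5.6.1. The same added table would resolve the conflict.

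**A separate SAP may specify more.** No separate SAP text was available. Section 9.5.5.1 defers PFS rules to the SAP; section 9.5.6 makes no such deferral. For late events, an SAP table would have to depart from the stated rule. For laboratory grades and deaths, absence from 9.5.6 does not prove absence from the plan.

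**A table of related events rests on an open-label causality judgement.** This stands and limits what the table can show.

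A reader might infer three stronger points, which the documents do not support:

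- *That deaths attributed to progression are absent from every comparison between arms.* They count in OS and PFS. The phase 1 split of deaths in section 1.3.2.1.2 cannot size any omission: it covers all 256 patients, has no sunitinib arm and gives no timing relative to the last dose.
- *That laboratory grades, or grades from unscheduled visits, are excluded.* No section removes unscheduled results, and categorical laboratory summaries are promised. Counts of laboratory terms in the phase 1 TEAE table are findings that did reach an AE table, so they do not show omission.
- *That the whole safety comparison depends on the unblinded investigator.* Section 7.7.1 gives criteria for clinical significance, and the continuous laboratory, vital-sign and echocardiogram summaries do not depend on that judgement.

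**Conclusion.** The point holds for late events on the explicit text: suspected-related SAEs and AESIs after day 30 must be reported, belong to a stated safety endpoint, and are kept out of every AE table. Each patient affected is worth about 2 percentage points in an arm of 49, assuming all are dosed and the patient had no earlier event of the same type. The number of such patients is unknown and may be small. The primary PFS analysis is untouched, and no safety hypothesis is tested. This is a cheap improvement to reporting, not a flaw that threatens the trial.

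For laboratory grades and deaths by cause the plan is silent rather than excluding, so these are secondary suggestions only. They rest on section 9.5.6 being the full safety analysis text.

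**What to change.** **Main change, section 9.5.6.1.** Keep the TEAE tables as planned. Add a by-arm table of all treatment-related SAEs and AESIs whenever they occur, with events more than 30 days after the last dose in a separate column. Use the safety population and the relatedness rule in section 7.3. A footnote should say that late events depend on the open-label investigator's causality judgement, and that follow-up after treatment may differ between arms and includes no scheduled skin examination.

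**Secondary suggestions.**

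- Section 9.5.6.6: state that CTCAE grade will be shown by arm as a shift from baseline to worst post-baseline grade, including unscheduled results.
- Section 9.5.6: add a by-arm summary of deaths from first dose to 30 days after the last dose, by cause, including those attributed to progression.

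**Cost.** One extra table for the main change and two for the suggestions, all from data already collected. No visit, procedure or reporting rule changes. The new late-event table does not remove the dependence on causality judgement or the unequal follow-up after treatment.

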9.5.7. Pharmacokinetic analysis

Plasma concentration of DCC-2618 (ripretinib, ZL-2307) and its metabolite DP-5439 will be summarized by descriptive statistics. If the dose changes, plasma concentration can be summarized by dose level.

9.5.8. Biomarkers and pharmacodynamics analysis

Observe baseline KIT and PDGFRA mutation in plasma and features of mutation allele frequency change during the study

The Mann-Whitney U test will be used to analyze statistical difference between treatment groups in terms of treatment effectof DCC-2618 (ripretinib, ZL-2307) and sunitinib on mutation frequency tested using ctDNA at all time points. Formal hypothesis test will not be performed.

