1.3.2.2. Clinical Pharmacokinetics and Pharmacodynamics Markers

In the non-clinical study, it has been confirmed that DP-5439 is an active metabolite of DCC-2618 (ripretinib, ZL-2307) and its activity features are similar to DCC-2618.

Plasma $T_{1/2}$ of metabolite is longer (30 - 60 hours), indicating QD dosing schedule is feasible. Sub-study of food influence revealed that DCC-2618 (ripretinib, ZL-2307) taken with diet didn't have negative influence on absorption. Please refer to Section 1.5.2 for more information of basis of current study dose, dosing schedule and treatment duration.

In GIST paitents who have previously received multiple therapies, DCC-2618 (ripretinib, ZL-2307) could rapidly eliminate extensive KIT mutation in plasma DNA. In general, on Day 15 of Cycle 1, total plasma concentration (C_{max}) at the start dose of 100 mg BID was very high, more than 5 am (3,000 ng/mL); the observed mean exposure was far more than the target plasma level, including exposure level for KIT mutations (V654A and T670I) most insensitive to inhibiting DCC-2618 (Ripretinib, ZL-2307).

In the phase 1 study, next-generation plasma cell-free DNA (cfDNA) sequencing was carried out in GIST patients at baseline, Week 2, during patients' participation in the study and at the end of study (Figure 3). Mutations were tested and quantified with Guardant 360 v2.9 or v2.10. According to preliminary data (cut-off 18 April 2018), circulation tumor DNA (ctDNA) was tested in most baseline cfDNA. In 131 GIST patients with KIT mutation, KIT mutation was detected in baseline ctDNA test of 95 patients and the mutation range covered exons 9, 11, 13, 14, 17 and 18 (Figure 3). Of 9 enrolled patients with PDGFRA exon 18 mutation, PDGFRA exon 18 mutation was only detected in ctDNA samples of 2 patients (if archived tissues are available, it will be confirmed by testing the tissues).

Figure 3: KIT mutation in baseline ctDNA of 131 GIST patients listed according to treatment line (n = 95)

Each list represents one GIST patient. Each color bar in each line represents one or multiple mutations detected in KIT exons 9, 11, 13, 14, 17 and 18. In patients with KIT exon 9/11 mutations detected in baseline ctDNA, secondary mutation occurred in KIT exons 13, 14, 17 and 18 of second- to ≥ fourth-line patients

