2.3. Exploratory objectives

- To evaluate potential biomarkers in blood or tumor tissue which might predict response to DCC-2618 (ripretinib, ZL-2307)
 - To understand potential drug resistance mechanism to DCC-2618 (ripretinib, ZL-2307) in GIST.
 - To characterize KIT and PDGFRA mutations at baseline and DCC-2618 (ripretinib, ZL-2307)-driven longitudinal mutant allele frequency changes in plasma.

Note: Blood samples and tumor tissues for exploratory purpose will be collected after obtaining the approval of China Human Genetic Resources Administration Office.

3. Study Design

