3.1. Overview of Study Design

This is a randomized, open-label, multicenter phase 2 clinical study to compare the efficacy and safety of DCC-2618 (ripretinib, ZL-2307) to sunitinib in GIST patients who progressed on or were intolerant to first-line anticancer treatment with imatinib.

Approximately 98 patients will be randomized in a 1:1 ratio to DCC-2618 (ripretinib, ZL-2307) 150 mg QD by continuous administration or sunitinib 50 mg QD, 4 weeks on, 2 weeks off. Up to 10% of randomized patients may have KIT/PDGFRA WT GIST (wild-type KIT and wild-type PDGFRA regardless of the mutational status of any other gene).

Randomization will be stratified by:

• KIT exon 11 mutation; KIT exon 9 mutation; other (KIT/PDGFRA WT or other KIT [lacking exon 9 or 11]/PDGFRA mutation);

The primary endpoint of the study will be evaluated using the modified Response Evaluation Criteria in Solid Tumors (RECIST) Version 1.1-GIST-specific based on independent radiologic review.

Upon disease progression by RECIST-GIST-specific based on independent radiologic review, patients will discontinue their assigned treatment.

If the investigator doesn't hope to confirm by the independent radiologic review or hopes to terminate the patient's treatment according to progressive disease based on "RECIST v1.1-GIST-specific Criteria" before obtaining results of the independent radiologic review, it is necessary to discuss with the sponsor.

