9.2.3. Exploratory endpoint

- KIT/PDGFRA mutation of tumor tissues at baseline and specific time points (e.g., resection of metastasis or progressive disease during the study).
- KIT/PDGFRA mutations and mutant allele frequency at baseline and the treatment effect of DCC-2618 (ripretinib, ZL-2307) on KIT/PDGFRA mutant allele frequency (MAF).

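### The ctDNA comparison in section 9.5.8 is not referred to each patient's baseline and has no rule for patients with no detectable plasma mutation at C1D1

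*Combined protocol and SAP*

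**What the plan says.** The exploratory objective (protocol section 2.3) concerns "longitudinal mutant allele frequency changes in plasma". The endpoint in section 9.2.3 covers mutations and MAF at baseline and the effect of treatment on MAF.

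Section 9.5.8 is the whole analysis text. Its first sentence describes baseline mutations and "features of mutation allele frequency change during the study". It then states: "The Mann-Whitney U test will be used to analyze statistical difference between treatment groups", applied to "mutation frequency tested using ctDNA at all time points". It closes with "Formal hypothesis test will not be performed".

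Three other places bear on this:

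- Section 9.3 defines six analysis populations, none of them for ctDNA. Section 9.4 gives rules for partial or missing dates only.
- Section 1.3.2.2 reports that among 131 KIT-mutant phase 1 patients "KIT mutation was detected in baseline ctDNA test of 95 patients", and that a PDGFRA exon 18 mutation was found in the plasma of 2 of 9 patients. Section 3.1 adds: "Up to 10% of randomized patients may have KIT/PDGFRA WT GIST".
- The plasma sampling note to Table 1 schedules a C1D1 sample and then one at centrally confirmed progression or at the end-of-treatment visit.

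**The concern.** A change in MAF can be measured only in a patient whose mutation is visible in plasma at baseline. The plan does not say which patients are compared, how a non-detect is scored, or whether the compared quantity is the raw frequency or the change.

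A rule is needed on either reading. If raw frequency is compared, a zero at the later sample can mean that the mutation was never measurable or that it was cleared. These are different facts with the same rank. If change is compared, a ratio to a zero baseline is undefined, and an absolute change scores a patient who stays undetectable as unaffected. Two analysts could follow section 9.5.8 and reach different answers from the same data. Read literally, all time points also include C1D1, where no treatment effect can exist.

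At stake is how the exploratory biomarker result is read: whether a difference in MAF change is visible, and whether a chance imbalance in detectable patients could be mistaken for one.

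**Working it through.** **Share undetectable at baseline.** The inputs are 95 of 131 KIT-mutant patients detected and 2 of 9 PDGFRA exon 18 patients detected (section 1.3.2.2), the 10% wild-type cap (section 3.1) and 98 patients.

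- KIT-mutant only: (131 - 95)/131 = 36/131 = 27.5% (exact 95% CI 20.0-36.0%).
- With wild-type at its cap: 0.90 × 0.275 + 0.10 = 34.7%.
- With the PDGFRA patients pooled: (36 + 7)/140 = 30.7%, and at the cap 0.90 × 0.307 + 0.10 = 37.6%.

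**Patients left to compare.** 98 × (1 - 0.275) = 71 and 98 × (1 - 0.347) = 64, if every one of them has a later sample. Patients still on treatment will not have one at the primary cut-off. If only the 58 patients with PFS events had a second sample, the numbers are 58 × 0.725 = 42 and 58 × 0.653 = 38.

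**Effect on power.** The plan states no power for this endpoint, so there is no figure to reproduce. MAF spread and effect size are not in the documents, so the following are assumptions: log-normal baseline MAF with log SD 1.0 to 2.0; SD 1.0 for the within-patient log change; a 2-fold shift between arms; baseline non-detects staying at zero; no assay detection limit; every patient sampled twice; 49 per arm. The table gives the simulated chance of two-sided p < 0.05 by Mann-Whitney, with 1,500 runs per row.

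| Undetectable | Log SD | Raw, everyone | Raw, detectable | Log ratio, detectable | Log ratio, non-detects scored as no change |
|---|---|---|---|---|---|
| 27.5% | 1.0 | 22% | 50% | 78% | 74% |
| 27.5% | 1.5 | 14% | 32% | 81% | 76% |
| 27.5% | 2.0 | 11% | 24% | 79% | 74% |
| 34.7% | 1.0 | 16% | 45% | 73% | 67% |
| 34.7% | 1.5 | 12% | 30% | 77% | 69% |
| 34.7% | 2.0 | 11% | 21% | 74% | 68% |

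The simulation error is about one point: √(0.78 × 0.22/1,500) = 0.011. A repeat gave 10-22% and 75-82% for raw in everyone and log ratio in detectable patients. With 35 per arm those two columns fall to 9-17% and 59-66%. For a 4-fold shift at 49 per arm they are 23-64% and about 100%.

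**Where the loss comes from.** Take 27.5% undetectable and log SD 1.5.

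- Dropping the baseline reference within detectable patients costs 81 - 32 = 49 points. Adding the non-detects costs 32 - 14 = 18 more.
- In the other order, scoring non-detects as no change costs 81 - 76 = 5 points, and dropping baseline then costs 76 - 14 = 62.
- With no undetectable patients at all, raw frequency has 45% power and the log ratio 92%.

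The missing baseline reference is the larger cause in either order. At log SD 1.0 the first order splits the loss about evenly (78 - 50 = 28 and 50 - 22 = 28).

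**If the effect is clearance.** Here the later sample is undetectable in 20% of one arm and 50% or 60% of the other (2,000 runs, log SD 1.5, 49 per arm).

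| Undetectable at baseline | Clearance | Raw, everyone | Raw, detectable | Loss |
|---|---|---|---|---|
| 27.5% | 20% vs 50% | 52% | 61% | 9 points |
| 27.5% | 20% vs 60% | 80% | 87% | 7 points |
| 34.7% | 20% vs 50% | 45% | 53% | 8 points |
| 34.7% | 20% vs 60% | 72% | 83% | 11 points |

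The ratio to baseline in detectable patients is within one point of the raw-detectable column.

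**The case against.** A reader might infer that the plan, run as written, scores undetectable patients as zero, tests raw frequency in everyone and so would largely hide a drug effect. The documents do not support that. Nothing in section 9.5.8 says that non-detects or wild-type patients enter the test or are scored zero. The sentence on MAF change and the objective in section 2.3 make a change analysis at least as natural a reading. The large loss also depends on an assumed shift and spread, and it does not appear for clearance, which is the kind of effect section 1.3.2.2 describes.

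Other objections also have weight. The 27-35% range is derived, from preliminary phase 1 data across treatment lines. That assay need not be the one used here, and the wild-type cap may not be reached. The simulation takes a second sample from everyone, whereas the trial draws it at progression or end of treatment. The endpoint is exploratory with no formal test, so power is only a rough measure of harm. The statistical section refers to a separate SAP that is not in the supplied text and might hold a rule, although section 9.5.8 does not defer to one.

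These points limit the size of the problem but do not remove the gap. Neither reading of section 9.5.8 works without a stated rule. The clearance in section 1.3.2.2 is described as rapid, and phase 1 sampled at Week 2, so samples at progression or end of treatment may not capture it.

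**Conclusion.** The concern holds in a limited form. Section 9.5.8 names a comparison of mutation frequency without a baseline reference, an evaluable set or a score for non-detects, while the objective is change. On the protocol's phase 1 figures, about 27% of KIT-mutant patients would be undetectable at C1D1. The overall share is about 35% with wild-type at its cap, or about 38% if the PDGFRA result is pooled in.

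If raw frequency were tested in everyone, a proportional shift could be missed. That is conditional on the reading and on the assumed spread and effect. It should not be restated as a finding that the plan would hide a drug effect, nor blamed mainly on the undetectable patients, since most of the loss is the unused baseline. The matter is worth tidying before data are seen, so that the choice between analyses that can disagree is not made afterwards. It has no bearing on the primary PFS result.

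**What to change.** In section 9.5.8:

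- Compare arms on the log ratio of post-baseline to C1D1 MAF, in patients with at least one KIT/PDGFRA mutation detected at C1D1 and a later sample.
- Set post-baseline non-detects to the assay's detection limit.
- State which MAF is used when a patient has several mutations.
- Report clearance alongside.
- List patients undetected at baseline by arm and genotype, including any whose mutations emerge later, because these bear on the resistance objective.
- Label the p-value descriptive, so that the named test and the statement "Formal hypothesis test will not be performed" agree.

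The cost is wording only, with no new samples. The comparison would apply only to patients with detectable baseline ctDNA. At the primary cut-off the usable number will be below the 64-71 computed above, and roughly 38-42 if only the 58 patients with PFS events have a second sample.
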